5. Placebos are quarantined until they have passed bioburden testing, as outlined in section XII below.
6. Doses are transferred into the final pharmaceutical bottle packaging. The dosage size depends upon the requirements of an individual clinical trial's specifications. Clinical trial specifications vary with the trial protocol, objectives, and the indication being targeted.

Labeling

See Drug Master File (15543).

IV. STUDY PROCEDURES

An outline of the study timeline and measurements is shown in Appendix 1

Overview. This is a randomized controlled pilot study to assess the safety of FMT in obese patients. Additionally, the study will measure the microbiological and clinical impacts of FMT in patients with obesity. We will continue to prospectively enroll adult who are obese (BMI of 35 kg/m² or greater) after providing written informed consent until 20 have completed all study visits. We anticipate total enrollment to be 50 patients to account for screen fails and dropouts. The study participants will be randomized 1:1 to either the treatment arm or the placebo arm. The treatment arm will receive an FMT induction followed by monthly (weeks 4 and 8) maintenance oral capsules for 12 weeks. The placebo group will receive placebo capsules at the time of their induction followed by monthly intake of oral placebo capsules for 12 weeks. The participants will not receive dietary instruction and will be asked to continue with their regular diet. Information about their dietary habits will be collected at each study visit. Donor Stool and placebo material will be obtained from OpenBiome. OpenBiome, with whom we have previously collaborated with, is a nonprofit 501(c)(3) organization that provides hospitals with screened, filtered, and frozen material ready for clinical use.

A. Recipient Procedures

Week -2: Screening – potential subjects will undergo the following screening procedures one to two weeks prior to FMT to determine if they meet the recipient selection criteria;

1. Repeat of Medical record review to confirm diagnosis and treatment history if questions remain after initial screen. This will include either review of partner's available data or data provided from home provider (When applicable)
2. Symptom assessment (Symptom Diary Card) and physical exam by study physician
3. Anthropometric measurements: BMI, Iliac measurements, waist-to-hip ratio

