4. Baseline blood work to assess for sequela of obesity: insulin, LFTs, CBC, and HgA1C and fasting serum lipids and blood glucose
5. Stool sample to exclude current infections (bacterial culture, ova & parasites, Clostridium difficile toxin) and a sample for high-throughput 16S rRNA sequencing and metabolomics.
6. Urine Pregnancy Test for females of child-bearing age: Women of child-bearing potential will be counseled by study clinicians that those randomized to the treatment arm will be requested to avoid pregnancy by hormonal or barrier methods from randomization for 4 months (duration of FMT therapy and one month lag afterwards).
7. Diet recall and question about specific dietary restrictions or preferences. The patients will be asked to maintain their standard diets throughout the study.
8. Baseline levels of ghrelin, Leptin, PYY and adiponectin will be measured
9. A mixed meal tolerance test will also be performed. GLP-1, leptin and PYY measurements will be taken at time 0, 15, 30, 45, and 60 minutes.
10. Pre FMT screening labs including HIV, Hepatitis B and C and Syphilis
11. Serum will also be collected for metabolomic profiling
- 12: Test swallow of an empty capsule
13. Indirect Calorimetry – see Appendix 7
14. Patients will be sent home with 9 doses of a proton pump inhibitor to be taken 48 hours 24 hours prior to and the day of each capsule administration (3 times total).

Week 0: (Treatment and Control Arms): Randomization: Eligible patients will be randomized 1:1 according to a computer-generated randomization list. The randomization will be held centrally at the Brigham and Women's Hospital Research Pharmacy. The treatment location will be masked to the patient and investigators performing data analysis. The health care worker administering FMT or placebo will not be aware of the treatment being administered. Treatment will be administered based on the result of randomization.

- Food Frequency Questionnaire
- Stool transplant (or Placebo) via capsule induction
- A proton pump inhibitor will be taken daily at 48 hours and 24 hours prior to and day of capsule consumption.

Week 1: (Treatment and Control Arms): Follow up and adverse event screening. Additionally:

- BMI, Iliac measurements, hip to waist ratio
- Indirect Calorimetry
- Stool for microbiome analysis and metabolomics
- CBC, LFTs, FBG, HgA1C, lipids, glucose, metabolomics
- diet recall
- Symptom Diary Card and Adverse Event screening

Weeks 2-12: (Treatment and Control Arms)

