Symptom diary Cards will be filled out weekly for adverse event monitoring

Week 4, 8 (Treatment and Control Arms): Monitored Capsule Consumption and Follow-up study visits for assessment of:

- Ingestion of 12 FMT capsules or inactive placebo.
- A proton pump inhibitor will be taken daily for the 48 hours 24 hours prior to and day of capsule consumption.
- BMI, Iliac measurements, hip to waist ratio
- Stool for microbiome analysis and metabolomics
- CBC, LFTs, FBG, HgA1C, lipids, glucose, metabolomics
- diet recall
- Symptom diary Card and Adverse Event screening

Weeks 6, 12 : Follow-up study visits for assessment of:

- BMI, Iliac measurements, hip to waist ratio
- Stool for microbiome analysis and metabolomics
- CBC, LFTs, FBG, HgA1C, lipids, glucose, metabolomics, ghrelin and leptin, PYY and adiponectin
- Mixed meal tolerance test followed by serum for GLP-1, Leptin and PYY at time 0, 15, 30, 45, and 60
- diet recall
- Indirect Calorimetry
- Symptom Diary Card and Adverse Event screening

Week 26 and 52:

- Safety assessment and Symptom Diary Cards via phone interview by a physician to screen for adverse events.
- Stool sample for microbiome analysis to be mailed in
- Ask for the patients current weight

Stool collection instructions are outlined in Appendix 2.

Patient obligations in the study will end at week 52 however the patient's medical record may be followed prospectively for evaluation of weight loss and weight loss surrogates as well as metabolic parameters done for clinical care through year 5 post-enrollment as needed. This may include review of partner's available records or records from home provider. (when applicable)

Stopping Criteria

Adverse events will be specifically monitored at week 1, 4, 6, 8, 12, 26, and 52 after FMT by direct patient interviews, or by reporting from clinical sites of adverse events at any time in-between. A data safety and monitoring board (DSMB, Appendix 5) will review all patient data to ensure optimal patient safety and precautions for subjects with obesity treated with FMT. A severity grade for adverse events (Appendix 6) and subject symptom diary cards will be used (Appendix 7). The DSMB will meet a minimum of 2 times: after treatment of the first 10 subjects, and after treatment of all 20 subjects. Study will be stopped under the following circumstances;

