9. Use of any weight loss medication or participation in a weight loss study or program such as Weight Watchers in the past 3 months
10. History of recent weight change (weight loss or weight gain in the two months preceding trial enrollment). This is defined as a gain or loss of 10 or more pounds in the preceding 2 months.
11. Patients who are pregnant or breastfeeding
12. Patients who are unable to give informed consent
13. Patients who have previously undergone FMT
14. Patients who have a confirmed active malignancy or cancer
15. Patients who are immunocompromised including HIV infection.
16. Participation in a clinical trial in the preceding 30 days or simultaneously during this trial
17. Previous gastric or small intestinal surgery that alters gut anatomy such as fundoplication, gastric resection, gastric bypass, small bowel resection, and ileocectomy
18. Other comorbidities including: systemic lupus, inflammatory bowel disease, or Chronic kidney disease as defined by a GFR <60mL/min/1.73m² 44 or rheumatoid arthritis
19. History of rheumatic heart disease, endocarditis, or valvular disease due to risk of bacteremia from colonoscopy
20. Any condition, based on clinical judgment that may make study participation unsafe
21. History of severe food allergies (e.g. anaphylaxis or anaphylactoid reaction)
22. Use of immune modulators including methotrexate, mycophenolate mofetil, tacrolimus, cyclosporine, thalidomide, Interleukin-10, or Interleukin-11 or prednisone within the past 2 months
23. Treatment with infliximab, adalimumab, certolizumab, natalizumab, vedolizumab or thalidomide within the prior 2 months
24. Congenital or acquired immunodeficiencies
25. Patients with allergies to ingredients Generally Recognized As Safe (GRAS): glycerol, sodium chloride, hypromellose, gellan gum, titanium dioxide, cocoa butter
26. Dysphagia: oropharyngeal, esophageal, functional, neuromuscular (e.g. stroke, multiple sclerosis, ALS)
27. History of aspiration
28. History of severe gastroparesis

For patients outside of the Partner's system, medical diagnoses that are identified by the patient and relevant to inclusion and exclusion will be confirmed with their treating physician

Subject Withdrawal Criteria: Patients – patients will be withdrawn under the following circumstances:

1. Patient withdraws their consent for follow-up visits or contacts.
2. Patient is unable to successfully perform capsule test swallow.

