We will not utilize advertisement material or other informational materials for patients beyond the consent form. Patients will be given as much time as they need to decide. They will be given a copy of the consent form to take home, read, and consider, and they will be encouraged to discuss participation with family members and health care providers.

The consent form will be signed that day or at a future visit to the clinic. Once signed, the subject will undergo further screening to determine eligibility. No study related procedures will be performed until the informed consent form has been signed.

If they decide to participate, both study and controls will be asked to maintain their standard diet.

If patients reach out to us via the provided E-mail or phone number located at the clinicaltrials.gov website, we will pre-screen them using questions from the provided E-mail/phone script. If the patient's responses do not indicate any exclusion criteria being met, then we will contact their primary care provider via email or phone call (with patient permission) to confirm medical diagnosis. Once patient's medical and treatment history are thoroughly vetted with the primary care physician, we will ask the physician to further discuss the study with the patient to minimize "undue influence" and ensure appropriateness for participation. When we are given the approval of the physician to enroll the patient in the study, we will then schedule the standard screening visit to re-review medical history (inclusion and exclusion criteria) and perform informed consent. (See below) If the patient has no medical problems and has no treating physician due to lack of medical problems, the patient will be eligible to come in for a screening visit.

Consent Procedures:

The treating physician will introduce the study to the potential patient and request the patient's permission to be approached by study staff. With the treating physician's permission, either a physician investigator or study coordinator will describe the research study in detail, including participation and risks and alternative courses of treatment, and answer any questions or concerns that the patient may have. Patients will be given as much time as they need to consider participation before signing the consent form.

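### Exclusion 18 sets a GFR limit, but the listed screening tests include no creatinine or eGFR, so unrecognised chronic kidney disease could be missed

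*Combined protocol and SAP*

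**What the plan says.** Section V, exclusion 18, lists several comorbidities, among them "Chronic kidney disease as defined by a GFR <60mL/min/1.73m²".

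Section IV.A (Week -2 screening) sets out the tests used to decide eligibility. Item 4 is "Baseline blood work to assess for sequela of obesity: insulin, LFTs, CBC, and HgA1C and fasting serum lipids and blood glucose". Item 8 adds gut and fat-tissue hormones, item 9 a mixed meal test, item 10 "Pre FMT screening labs including HIV, Hepatitis B and C and Syphilis", and item 11 states that "Serum will also be collected for metabolomic profiling".

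At weeks 1, 4 and 8 the blood list is "CBC, LFTs, FBG, HgA1C, lipids, glucose, metabolomics". Weeks 6 and 12 use the same list with hormones added.

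Medical history reaches the study team by other routes. Screening item 1 is "Repeat of Medical record review to confirm diagnosis and treatment history if questions remain after initial screen". Section VI (Recruitment Procedures) has a referring or primary care physician vet the patient, with one exception: "If the patient has no medical problems and has no treating physician due to lack of medical problems, the patient will be eligible" to attend a screening visit.

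**The concern.** The criterion is defined by a quantity that has to be measured, yet no listed test measures it. Someone whose reduced GFR has never been detected has no diagnosis to report and none for a physician to confirm. That person meets a stated exclusion, but nothing in the listed procedures would show it before randomisation.

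The stake is eligibility in a trial whose main objective, according to Section VIII, is safety. The sponsor chose to keep patients below this limit out of the study. As written, the plan cannot show that it did so for undiagnosed cases.

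**Working it through.** No sample size, power or error rate is involved, so the check sets the exclusions beside the procedures.

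**Step 1. Exclusions with a numeric blood-test limit, against the Week -2 list.**

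| Exclusion (Section V) | Limit | Matching screening test (Section IV.A) |
|---|---|---|
| Item 1 | Triglycerides > 500 mg/dL | Fasting lipids, item 4 |
| Item 6 | LFTs > 3x ULN | LFTs, item 4 |
| Item 8 | HbA1C > 10% (type 2 diabetes on oral medication) | HbA1C, item 4 |
| Item 18 | GFR < 60 mL/min/1.73m² | None listed |

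Three of four are backed by a listed test; one of four is not.

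**Step 2. Could another listed test supply GFR?**

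- Item 4 is limited to "insulin, LFTs, CBC, and HgA1C and fasting serum lipids and blood glucose".
- Item 10 is worded as an open list, but every test it names is for infection.
- The metabolomic serum in item 11 is not described as an eligibility test.
- The blood lists for weeks 1, 4, 6, 8 and 12 name no renal test. They also fall after randomisation and so could not serve eligibility.
- Creatinine appears in the documents only as a row of the Appendix 4 toxicity table, which schedules nothing.

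**Step 3. Could the history routes supply it?**

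| Route | What it can show | GFR value required? |
|---|---|---|
| Record review (Section IV.A, item 1) | Diagnosis and treatment history, if questions remain | No |
| Physician referral or vetting (Section VI) | Conditions known to the physician | No |
| Physician confirmation for patients outside the hospital's own system (end of exclusion list, Section V) | Diagnoses the patient has reported | No |
| Laboratory values from the health record (Section IV, data recorded on CRFs) | A past creatinine, if one exists | No; no look-back period is set |
| Exclusion 20, clinical judgment | What the clinician knows or suspects | No |

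Each route can identify known disease. None makes a GFR value a condition of entry.

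**Step 4. The patient with no treating physician.** Section VI lets this patient attend screening without physician vetting. The patient then undergoes the listed tests, none of them renal, and may have no earlier result on file. For this patient both Step 2 and Step 3 may yield nothing.

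**The case against.** **Absence is shown only for the listed tests.** Section IV refers to Appendix 1 for the outline of measurements, and the content of that appendix is not in the available text. A renal test could be listed there, and screening item 10 is formally open. This stands and limits the conclusion. If Appendix 1 does list such a test, what remains is an inconsistency with Section IV.A.

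**Item 18 may be a diagnosis criterion.** It groups kidney disease with lupus, inflammatory bowel disease and rheumatoid arthritis, for which no specific screening test is listed either. On that reading the GFR figure only says what counts as kidney disease, and the criterion works for documented cases. This is a fair reading and the documents do not rule it out. But item 18 does not say known or documented, and kidney disease is the only condition in it given a numeric definition. HbA1C in item 8 is a close parallel: it is a limit set within a comorbidity criterion, and it does have a screening test.

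**There are several routes to renal status.** A reader might infer that record review is the only safeguard. It is not: Section VI has physicians vet the history, and laboratory values may be taken from the health record. These routes narrow the gap to unrecognised disease; they do not close it.

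**The no-physician route is narrow.** A reader might infer that such patients are enrolled unchecked. Section VI offers them only a screening visit, and only where they have no medical problems. They should not be merged with the patients with diabetes whom exclusion 8 still admits.

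**The protocol lists no renal risk.** Section IX names none, and no endpoint depends on GFR. That keeps the point modest, though it does not explain how a stated exclusion is to be applied.

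**Conclusion.** The point holds for the tests that are listed. Exclusion 18 uses a GFR limit with no listed test behind it, alone among the four numeric blood-test limits, and the history routes require no GFR value. An undiagnosed patient below the limit could be randomised and dosed without any departure from the written procedures. It merits correction before enrolment continues, but it does not undermine the design.

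The conclusion rests on two assumptions: that Appendix 1 adds no renal test, and that item 18 is meant to cover more than documented disease.

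Two stronger readings are not supported. First, a reader might want a figure for how many patients would be affected. The documents give no prevalence of unrecognised reduced GFR, so any such figure would rest wholly on an outside guess. Second, a reader might infer from the creatinine grades in Appendix 4 that creatinine should be measured throughout the study. Appendix 4 is a general toxicity table that also grades injection-site reactions, CD4 counts and troponin, so a row in it does not imply planned monitoring.

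**What to change.** Reconcile exclusion 18 in Section V with the screening list in Section IV.A, in one of two ways.

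- If the GFR limit is meant to apply to every patient, add serum creatinine with calculated eGFR to screening item 4, using blood already drawn, and require the result before randomisation. The existing limit stays as it is.
- If only documented kidney disease was intended, say so in item 18 and name the source, for example the health record or the treating physician. State also what applies to a patient who has neither.

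Check Appendix 1 at the same time. If it already lists a renal test, bring Section IV.A into line with it.

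The first option costs one inexpensive analyte, a change of wording and possibly an extra screen failure. The second costs wording only, but accepts that unrecognised disease will not be looked for.

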Hypothesis: Fecal microbiota transplantation will result in a sustained repopulation of the patient's microbiome that corresponds to the bacteria from the donor stool.

III. Methods and Study Design

This is a randomized controlled pilot study to assess the safety and to measure the microbiological and clinical impacts of FMT in patients with obesity. We will continue to prospectively enroll and screen adult patients until 20 patients have completed all study visits. We anticipate total enrollment to be 50 patients to account for screen fails and dropouts. Eligible patients are those who are obese (BMI of 35 kg/m² or greater). Patients will be randomized 1:1 to receive FMT or placebo. The participants will receive either an FMT from a lean healthy donor using 30 induction FMT capsules or placebo capsules. The participants will continue to receive a monthly maintenance dose of 12 FMT oral capsules or placebo at week 4 and week 8. Serum for hormone levels will be collected at baseline, weeks 1, 4, 6, 8 and 12. Stool for microbial assessment will be collected at baseline and weeks 1, 4, 6, 8, 12, 26, and 52. A Food Frequency Questionnaire will be taken by the patient at week 0. Donor Stool will be obtained from OpenBiome. OpenBiome is a nonprofit 501(c)(3) organization that provides hospitals with screened, filtered, and frozen material ready for clinical use (See Attachments for OpenBiome Quality and Safety Program as well as donor screening examples).

Primary Safety Endpoint:

Safety Endpoints: Number and nature of adverse events at week 1, 6, 12 and 26.

Primary Clinical Endpoint:

The primary clinical end point is an increase in the AUC for GLP-1 after a mixed meal test from baseline and 12.

Secondary Endpoints:

- Microbial Endpoints: Recipients fecal microbial diversity at week 6 and 12 compared to baseline
- Clinical Endpoints: Decrease in BMI and waste circumference at week 6 and 12 compared to baseline.

Trial Treatment:

The treatment for this trial will be administration of an induction dose of 30 FMT capsules ingested orally. Treatment will occur after screening.

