- Any unexpected serious adverse events occur that the DSMB determines as at least possibly related to FMT or detection of new pathogenic intestinal infection in stool samples in any patient treated.

Any subject who develops a serious adverse event that is judged to be probably, possibly, or definitely related to FMT therapy will receive no further FMT treatment. They will remain in the trial only for adverse event follow-up.

Accountability Procedures for the Investigational Product

The location, volume and number of all FMT donor solutions will be maintained in a log by the research team. The principal investigator will be responsible for accurate record and tracking of all FMT solutions. Logging of FMT solution used for administration will be performed using a two-person process.

Data to be Recorded Directly on the CRFs

Data will be obtained from patients directly, and their electronic health record as follows;
Demographics , age, gender, co-morbidities, medication use, and laboratory values.

Donor Procedures (OpenBiome):

Prior to enrollment, donors (age >18), receive informed consent with oversight from MIT's IRB and COUHES. Donors are interviewed by a healthcare professional to determine whether they meet the following:

Clinical Exclusion criteria:

1. Infectious risk factors:

- Known HIV, Hepatitis B or C infections or exposure within previous 12 months
- High risk sexual behaviors
- Use of illicit drugs
- Tattoo or body piercing within previous 6 months
- Incarceration or history of incarceration
- Known current communicable disease
- Risk factors for variant Creutzfeldt-Jakob disease
- Travel within previous 3 months to countries where risk of infectious diarrhea is elevated

2. Gastrointestinal and systemic comorbidities:

- History of IBD, irritable bowel syndrome, chronic constipation or chronic diarrhea
- History of gastrointestinal malignancy or known polyposis
- Antibiotic use within the previous 3 months
- Immunosuppressive state or use of immunosuppressive medications
- History of major gastrointestinal surgery (e.g., gastric bypass)
- Metabolic syndrome ; history of NAFLD, hypertension, dyslipidemia, CAD, CHF
- Systemic autoimmunity, e.g., multiple sclerosis, connective tissue disease
- Atopic diseases including asthma and eczema, eosinophilic disorders of the gastrointestinal tract
- Chronic pain syndromes, e.g., chronic fatigue syndrome, fibromyalgia

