3. These above patients will only be followed-up for week 2 adverse event screening, as they will not have received FMT. These subjects will be replaced, as they will not be considered “treated”

VI. SUBJECT ENROLLMENT

Recruitment Procedures:

BWH gastroenterologists and Primary Care Physicians, including attending physicians and fellows, will be informed of the study's aims and inclusion criteria. These doctors who have firsthand knowledge of the patient's medical history must give approval for his/her patient to be contacted for research purposes and will inform the principal investigator of patients who meet the study criteria and who may be good candidates for the study. The referring physician will introduce the study to the potential patient and request the patient's permission to be approached by study staff.

After the treating physician has described the research study to the patient and has given permission to be contacted, a member of the study staff will be available for any follow-up questions. Investigators and study coordinators will reinforce with any potential subjects that participation is voluntary, that they do not have to participate, and the decision not to participate will not affect their care now or in the future. The patient will be given a copy of the informed consent, and encouraged to discuss the study with family, friends, their PCP, and/or others. Study staff will follow up to see if there are any questions or concerns that have not been addressed. These follow-up contacts will reoccur until the patient has either (a) been enrolled or (b) turned down participation in the study.

To minimize the “undue influence” that the principal investigator may have on study subjects, [name] patients (whom she feels are eligible) will be initially approached by another physician or nurse practitioner in the practice about the study. Subjects will be approached by a study staff member (investigators, research assistant or coordinators) when they have given their permission to be contacted. They will be given both oral information about the study and they will have the opportunity to ask questions of the study staff at the time of recruitment. Patients will also have an opportunity to discuss participation with their primary physicians, including [name], as well once they have received all study information.

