In order to avoid coercion, study staff will reinforce that participation is voluntary and that their decision will not affect the medical care that they receive now or in the future. If patients seek more time to consider participation, they will be given a copy of the consent form and encouraged to discuss the study with family, friends, PCP, or others. Study staff will follow-up to see if any questions or concerns have not been addressed. A physician investigator will obtain informed consent signatures.

VII. Assessment of Safety

Patient safety monitoring schedule - although there have been no reported serious adverse events associated with fecal microbiota transplantation (FMT) in patients with recurrent refractory Clostridium difficile, we will have a special data safety and monitoring board (DSMB) to ensure optimal patient safety and precautions for subjects with obesity treated with FMT. Adverse events will be specifically monitored at 1, 4, 6, 8, and 12, weeks after FMT by direct patient interviews, or by reporting from clinical sites of adverse events at any time in-between. Adverse events will also be assessed via telephone calls at weeks 26 and 52. The DSMB will meet a minimum of 2 times: after treatment of the first 10 subjects, and after treatment of all 20 subjects. A copy of the DSMB charter is located in Appendix 3.

For this trial, an adverse event (AE) is defined as any untoward medical occurrence in a patient or clinical investigation patient administered a biologic product; such an occurrence does not necessarily have to have a causal relationship with this treatment. An AE can be any unfavorable and unintended sign, symptom, or disease temporally associated with the use of a medicinal product whether or not considered related to the medicinal product. A serious adverse event (SAE) is defined as any untoward medical occurrence that results in death, is life threatening, requires hospitalization or prolongation of existing hospitalization, results in persistent or significant disability/incapacity, is a congenital anomaly/birth defect, is an important medical event that may not be immediately life threatening or result in death or hospitalization but may jeopardize the patient or may require intervention to prevent one of the other outcomes previously mentioned. Adverse events will be determined by a toxicity grading scale (Appendix 4).

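### Withdrawal item 3 treats every patient who withdraws consent as never dosed and not treated, which is false after a capsule dose and could delay the DSMB reviews that are timed by the treated count

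*Combined protocol and SAP*

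**What the plan says.** The Subject Withdrawal Criteria in Section V have three numbered items. Item 1 is withdrawal of consent: "Patient withdraws their consent for follow-up visits or contacts". It sets no time limit. Item 2 is inability to swallow the test capsule. Item 3 then covers both groups: "These above patients will only be followed-up for week 2 adverse event screening, as they will not have received FMT". It goes on: "These subjects will be replaced, as they will not be considered" treated.

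The test swallow belongs to the week -2 screening list in Section IV (item 12: "Test swallow of an empty capsule"). Study capsules are taken at Day 0, week 4 and week 8.

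The Stopping Criteria in Section IV, Section VII and the DSMB charter (Appendix 3, section 3) all set two minimum DSMB meetings by number treated: the first 10, then all 20. The charter holds the study at each point until the board agrees to continue.

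The safety endpoint in Section III is "Number and nature of adverse events at week 1, 6, 12 and 26", with no population named. Section VIII calls safety the main objective and defines no analysis set.

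**The concern.** Item 3 is a rule about who counts as exposed, and its wording reaches people who were exposed. A patient can take 30 induction capsules, withdraw consent the next week, and fall under a sentence that says no FMT was received. In a pilot that stops enrolling at 20 completers, one such patient is a visible share of the exposed group.

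The treated count has a practical use: it triggers the scheduled DSMB reviews. If dosed withdrawers are not in it, the board's first planned look comes after more people have been dosed than the plan intends. Because no safety population is defined anywhere, nothing in the statistical section corrects the classification.

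**Working it through.** The plan states no figure on this point, so there is none to reproduce. The check is mainly a reading of the text.

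**1. Whom item 3 reaches.** It applies to items 1 and 2 together. For item 2 the claim of no exposure is true, because the test swallow precedes any dose. For item 1 it is true only of withdrawal before Day 0. Item 1 speaks of follow-up visits, and Section IV uses that term for the visits after dosing (weeks 1, 4, 6, 8 and 12), so item 1 naturally includes dosed patients. Item 3's reason is also literally true of every dosed placebo patient, so it cannot mark exposure to study product in both arms.

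**2. Whether another rule covers a dosed withdrawer.** The Stopping Criteria have a rule for patients who stop FMT after dosing ("They will remain in the trial only for adverse event follow-up"), but only for serious adverse events judged related to FMT. No other section says how to classify a dosed patient who withdraws consent.

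**3. Whether the week 2 screening settles the timing.** It does not.
- Section VII counts weeks from dosing: "Adverse events will be specifically monitored at 1, 4, 6, 8, and 12, weeks after FMT by direct patient interviews". A patient who was never dosed has no such week 2.
- Week 2 is not an interview week. The contacts are weeks 1, 4, 6, 8 and 12, with telephone calls at 26 and 52. Week 2 has only the diary: "Symptom diary Cards will be filled out weekly for adverse event monitoring".
- A screening contact also sits badly with a patient who has withdrawn consent to contact.

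**4. What the treated count controls.** By wording it controls replacement and the DSMB meetings at 10 and 20. Replacement adds little, since enrolment runs until 20 patients finish whatever item 3 says. The DSMB timing is the remaining consequence.

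**5. Size of the shift.** Let d be the number of dosed patients, in either arm, who withdraw consent and are left uncounted before the tenth counted patient.

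Dosed at first review = 10 + d

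- d = 0: 10
- d = 1: 11
- d = 2: 12
- d = 3: 13

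The values of d are assumptions. Section III expects 50 enrolled for 20 completers, so 50 - 20 = 30, or 30/50 = 60%, are allowed for screen fails and dropouts together. It does not split the 30, or say how many would be dosed or would leave by withdrawing consent, so d cannot be derived.

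**The case against.** The strongest reply is that item 3 limits itself. Its reason is that no FMT was received, and a dosed FMT-arm patient does not meet that premise; sensible staff would not apply it. This probably describes the intent, and it is why the effect may be nil. It does not repair the text, which presents the premise as a fact about everyone in items 1 and 2.

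A second reply is that the safeguards are wide. The Stopping Criteria give the DSMB the data of every patient. Section VII sends all events to the board and the IRB, and has adverse events recorded on the CRF and summarised in the CSR. Two meetings are a minimum, and serious events go to the board whenever they occur. All of this stands and limits the harm.

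A third reply is that the trigger is loose anyway: the plan does not say whether treatment means the induction dose or the full course. That is so, and it is a separate ambiguity. It does not remove this one.

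A reader might infer three stronger things that the documents do not support.
- **That the safety analysis divides by the treated count.** Nothing says so. The endpoint is a number and description of events, and its population is simply undefined.
- **That events in dosed withdrawers are discarded.** No text removes events already collected. If all are kept, adding these patients to a denominator cannot raise the event rate, so the present wording cannot be said to flatter the safety result.
- **That item 3 contradicts the six-month follow-up of all subjects in Section VII.** The conflict is weak, because people who have withdrawn consent to contact cannot be followed under either wording.

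**Conclusion.** The point holds as a misclassification in a stated rule. Item 3 declares consent-withdrawers unexposed without limiting this to withdrawal before the first capsule, and no other section corrects it. The consequence that the documents support is a possible delay of the scheduled DSMB reviews: the first could fall after 11 to 13 people are dosed instead of 10, for an assumed 1 to 3 uncounted dosed withdrawers. This rests on a literal reading of item 3 and on at least one dosed patient withdrawing consent early enough. If either fails, there is no shift. The missing safety population is a real gap in Sections III and VIII. Item 3 does not cause it, but it leaves item 3 unchecked. The correction is worth making because safety is the main objective and the change costs almost nothing.

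**What to change.** - In item 3, limit the not-treated and replaced status to people who took no study capsule, active or placebo.
- In Section VIII, summarise safety in everyone who took at least one capsule, by product received, with adverse events included up to last contact or withdrawal of consent.
- In the Stopping Criteria, Section VII and the charter, count the DSMB triggers on that same set.
- Reconcile the week 2 follow-up wording in item 3 with the withdrawal of consent to contact in item 1 and with the adverse event schedule in Sections IV and VII.

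The cost is a short amendment, with no extra patients or visits. The DSMB reviews may fall slightly earlier when measured in completers.
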